#### 6.2. Part B

The study treatment names and ordering to be used in the TFLs are presented in Table 2.

**Table 2: Presentation of Study Treatments in TFLs (Part B)** 

Group	Study Treatment	Order in TFLs
B1 to B6	Placebo a	1
B1	XX μg OLP-1002	2
B2	XX μg OLP-1002	3
В3	XX μg OLP-1002	4
B4 b	XX μg OLP-1002	5
$\mathrm{B5^{b}}$	XX μg OLP-1002	6
B6 b	XX μg OLP-1002	7

<sup>a Placebo will be pooled across all groups

The TFLs will reflect the actual treatments received, and dose levels will be displayed in increasing order. The following footnote will be applied in all applicable Part B TFLs: "Dosing regimen was a single subcutaneous dose administered on Days 1, 4, 7, 10 and 13."

## 7. DEFINITIONS OF POPULATIONS

Any protocol deviations will be considered prior to database lock for their importance and taken into consideration when assigning subjects to populations.

<sup>b Groups to be included if required

<sup>b Groups to be included if required

SAP CONFIDENTIAL

# Covance Study: 8379789 Protocol Reference: OLP-1002-001

## 7.1. All Subjects Population

The all subjects population will include all subjects who signed the informed consent form (ICF) and had any study assessment recorded in the database per the protocol.

## 7.2. Safety Population

The safety population will include all subjects who received a dose of study treatment (OLP-1002 or Placebo).

## 7.3. Pharmacokinetic Population

The PK population will include all subjects who received a dose of study treatment (OLP-1002), have at least 1 quantifiable PK concentration, and have had no AEs or protocol deviations considered to impact PK.

## 7.4. Pharmacodynamic Population

The PD population will include all subjects who received at least 1 dose of study treatment (OLP-1002 or Placebo) and have at least 1 postdose PD assessment.

#### 8. STATISTICAL METHODOLOGY

#### 8.1. General

Listings will be provided for all data captured in the database, with the exception of medical history. Listings will include all subjects assigned to the all subjects population and include data up to the point of study completion or discontinuation. Any subject who discontinued the study will be identified accordingly in the listings. Summaries will include the subjects assigned to the relevant population based on data type.

Data analysis will be performed using the SAS® statistical software package Version 9.4 (or higher if upversioned during the study).

Analysis Data Model (ADaM) datasets will be prepared using Clinical Data Interchange Standards Consortium (CDISC) ADaM Version 2.1 (or higher if upversioned during the study) and CDISC ADaM Implementation Guide Version 1.1 (or higher if upversioned during the study). Pinnacle 21 Community Validator Version 2.2.0 (or higher if upversioned during the study) will be utilized to ensure compliance with CDISC standards.

Where reference is made to 'all calculations', this includes, but is not limited to, summary statistics, baseline derivation, changes from baseline, and any parameter derivations.

## 8.1.1. Calculation of the Summary Statistics

For continuous data the following rules will be applied:

- Missing values will not be imputed, unless specifically stated otherwise.
- Unrounded data will be used in the calculation of summary statistics.

• If number of subjects with valid observations (n) <3, summary statistics will not be calculated, with the exception of n, minimum, and maximum.

• As Early Termination data is not associated with any scheduled timepoint, it will be excluded from all calculations of summary statistics.

For categorical data the following rules will be applied:

- If the categories of a parameter are ordered (eg, AE severity), all categories between the possible minimum and maximum categories will be included, even if n = 0 for a given category. If the categories are not ordered (eg, race), only those categories for which there is at least 1 subject represented will be included.
- Missing values will not be imputed, with the exception of AEs where the 'worst-case' approach will be taken (see Section 8.7.1), or unless specifically stated otherwise. A 'missing' category will be included for any parameter for which information is missing. This will ensure that the population size totals are consistent across different parameters.

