## 8.1.3. Repeat and Unscheduled Readings

For vital signs and ECG data only, any predose value recorded in addition to the original value or a postdose value recorded within 15 minutes of the original value will be defined as a repeat value; any postdose value recorded more than 15 minutes after the original value will be defined as an unscheduled value. For all other data types (eg, laboratory parameters), any value recorded in addition to the original value will be defined as an unscheduled value.

The original value will be replaced by the last associated repeat value in all calculations, with the exception of the ECG outlier analysis (see Section 8.7.4).

As unscheduled values are not associated with any scheduled timepoint, they will be excluded from all calculations, with the exception of the baseline derivation (see Section 8.1.4) and ECG outlier analysis (see Section 10.7.4).

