## 8.7. Safety and Tolerability Assessments

#### 8.7.1. Adverse Events

All AEs will be coded using the Medical Dictionary for Regulatory Activities (MedDRA) Version 22.0 (or higher if upversioned during the study).

A treatment-emergent adverse event (TEAE) will be defined as an AE that starts during or after dosing (Part A) or the first dose (Part B), or starts prior to dosing (Part A) or the first dose (Part B) and increases in severity after dosing (Part A) or the first dose (Part B).

A treatment-related TEAE will be defined as a TEAE with a relationship of possibly related or related to the study treatment, as determined by the investigator.

All AEs will be listed. In addition to the data recorded in the database, the listings will include derived onset time and duration. Onset time will be calculated from the time of dosing TEAEs only.

The frequency of subjects with TEAEs and the number of TEAEs will be summarized for the following categories:

- TEAEs (overall, serious, leading to discontinuation, and leading to death) by treatment
- TEAEs by severity and treatment
- Treatment-related TEAEs (overall, serious, leading to discontinuation, and leading to death) by treatment
- Treatment-related TEAEs by severity and treatment

The frequency of subjects will be summarized separately for TEAEs and treatment-related TEAEs by the following:

- System organ class, preferred term, and treatment
- Preferred term and treatment
- System organ class, preferred term, day of onset, and treatment (Part B only)

For the AE data the following rules will apply:

- For the derivation of TEAE status: If the start date/time of an AE is incomplete or missing, an AE will be assumed to be a TEAE, unless the incomplete start date/time or the end date/time indicates an AE started prior to dosing (Part A) or the first dose (Part B).
- For the derivation of treatment-related TEAE status: If the study treatment relationship for a TEAE is missing, a TEAE will be assumed to be a treatment-related TEAE.

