## 8.7.4. 12-lead Electrocardiogram Parameters

All 12-lead ECG parameters, with changes from baseline will be listed; any value outside the clinical reference range will be flagged.

Summary tables and boxplots by treatment and timepoint will be provided for all 12-lead ECG parameters, with changes from baseline.

An outlier analysis will be performed for QT interval corrected for heart rate using Bazett's formula (QTcB) and QT interval corrected for heart rate using Fridericia's formula (QTcF). The analysis will include all individual original, repeat, and unscheduled postdose values.

The maximum postdose values will be summarized by treatment according to the following categories:

- ≤450 ms
- >450 and \( \le 480 \) ms (all instances flagged in the listing)
- >480 and \le 500 ms (all instances flagged in the listing)
- >500 ms (all instances flagged in the listing)

The maximum increases from baseline will be summarized by treatment according to the following categories:

- <30 ms
- >30 and  $\le 60$  ms (all instances flagged in the listing)
- >60 ms (all instances flagged in the listing)

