## 8.7.7. Other Assessments

All other safety and tolerability assessments not detailed in the above sections will be listed only.

Medical history will not be listed.

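### The QTc outlier analysis admits unscheduled ECGs but does not name Early Termination ECGs, so a literal reading can leave an exit ECG out of a worst-value table

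*SAP*

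**What the plan says.** Section 8.1.1 has two sets of rules. The first set opens with "For continuous data the following rules will be applied" and includes this one on Early Termination (ET) data: "As Early Termination data is not associated with any scheduled timepoint, it will be excluded from all calculations of summary statistics". The second set, for categorical data, does not mention ET data.

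Section 8.1.3 deals with unscheduled values. It also says that they have no scheduled timepoint, and then: "they will be excluded from all calculations, with the exception of the baseline derivation (see Section 8.1.4) and ECG outlier analysis".

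Section 8.7.4 defines what enters the QTcB and QTcF outlier analysis: "The analysis will include all individual original, repeat, and unscheduled postdose values". It then says: "The maximum postdose values will be summarized by treatment according to the following categories". The largest increases from baseline are categorised in the same way.

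On listings, Section 8.1 promises all data in the database except medical history, and says that listings "include data up to the point of study completion or discontinuation". Section 8.7.1 says "All AEs will be listed". Section 8.7.7 adds: "All other safety and tolerability assessments not detailed in the above sections will be listed only".

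**The concern.** ET values and unscheduled values are set aside for the same reason: neither has a nominal time. For a mean at a given hour that reason is enough. For a subject's worst value it has no force, because the table ignores when the value occurred. The SAP accepts this for unscheduled values and readmits them. It does not do so for ET values.

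The consequence would be uneven handling. A subject who stays in the study and has an extra ECG has it counted. A subject who leaves, and whose highest QTc is on the exit ECG, may not. Safety and tolerability are the primary objective, ECG parameters are a primary endpoint, and the dose groups are very small. Two programmers working from the same text could produce different outlier tables.

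**Working it through.** The SAP gives no figure to reproduce here. The check compares the rules and then sizes the effect of one subject.

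**Step 1: the rules side by side**

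| Value type | General rule | Exception for QTc outlier analysis | Named in 8.7.4 |
|---|---|---|---|
| Original | Used, unless replaced by a repeat (8.1.3) | Original kept as well | Yes |
| Repeat | Replaces the original (8.1.3) | All repeats kept | Yes |
| Unscheduled | Excluded, no scheduled timepoint (8.1.3) | Yes, explicit | Yes |
| Early Termination | Excluded, no scheduled timepoint (8.1.1) | None stated | No |

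The outlier analysis is evidently meant to take every postdose reading. ET is the only type for which this is not said.

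**Step 2: could an ET ECG count as unscheduled?** Section 8.1.3 defines a postdose unscheduled ECG as one taken more than 15 minutes after the original value. An ET reading need not have an original value to be measured against. If ET readings were already unscheduled, Section 8.1.3 would exclude them and the separate ET rule in Section 8.1.1 would be largely redundant. The reading is possible, but the text does not settle it.

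**Step 3: weight of one subject.** Inputs are from Sections 4.1 and 4.2.

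- Groups A1, A3, A5, A7 and A8 have 3 active subjects each: 1/3 = 33%.
- Groups A2, A4, A6, A9, A10, A11 and B1 to B4 have 6 active subjects each: 1/6 = 17%.
- Pooled placebo in Part A is 5×1 + 6×2 = 17 subjects: 1/17 = 6%.
- Pooled placebo in Part B is 4×2 = 8 subjects: 1/8 = 12.5%.

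These are the changes in a category percentage if one subject is placed in the wrong category.

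**Step 4: how often the question could arise.** The SAP gives no dropout rate, so 2%, 5% and 10% are assumptions. The chance of at least one early leaver among n active subjects is 1 − (1 − d)^n.

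| Assumed dropout d | n = 3 | n = 6 |
|---|---|---|
| 2% | 1 − 0.98³ = 5.9% | 1 − 0.98⁶ = 11.4% |
| 5% | 1 − 0.95³ = 14.3% | 1 − 0.95⁶ = 26.5% |
| 10% | 1 − 0.90³ = 27.1% | 1 − 0.90⁶ = 46.9% |

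These are upper limits for the problem itself. A table changes only if a leaver has an exit ECG, it gives that subject's highest QTc or largest increase, and it falls in a higher category than the earlier values.

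**The case against.** The best defence is that the ET rule does not reach this table. It sits under the continuous-data rules, while the outlier output is a count by category, and the categorical rules contain no ET exclusion. The rule also speaks of summary statistics, whereas Section 8.1 uses *all calculations* for a wider set that includes parameter derivations. An exit ECG might also be classed as original or unscheduled and enter that way. Finally, Section 8.7.4 asks for values above 450 ms and increases above 30 ms to be flagged in the listing.

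Most of this stands. It means that Section 8.1.1 cannot be said to bar ET values from the outlier table. It does not put them on the Section 8.7.4 list, and QTc is a continuous measurement until its maximum is categorised. What remains is an ambiguity with a possible, not a certain, omission.

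A reader might go further and infer that safety data from early leavers drop out of the outputs altogether. The SAP does not support that:

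- Their scheduled values before leaving stay in the summaries.
- Treatment-emergent adverse events are counted by subject and event, not by visit, and no ET exclusion applies to them.
- Section 8.1 lists all captured data and identifies subjects who discontinued.

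A reader might also infer that listings delete ET visits and later follow-up, for example 53 days for a Part B subject stopping at Day 4 (Day 57 − Day 4). The cut-off in Section 8.1 concerns leaving the study, not stopping treatment, and the ET visit can naturally be read as the point of discontinuation. The rule that all adverse events are listed, and the listing of assessments such as physical examinations under Section 8.7.7, point the same way. The cut-off is undefined, but no loss is shown.

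**Conclusion.** The point holds for the QTc outlier analysis. The exclusion of ET data is reasonable for by-timepoint summaries. The reason given for it does not apply to a per-subject maximum, and the list in Section 8.7.4 leaves the status of ET ECGs open when that of unscheduled ECGs is explicit. Read literally, an exit ECG can be missing from the worst-value tables.

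The size is one subject at a time: 33% or 17% of the active subjects at a dose level. This rests on the assumption that the ET visit includes an ECG, since the SAP does not say what ET assessments contain, and on the exit value being that subject's worst. The frequency cannot be stated without a dropout rate.

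The listing cut-off needs only a minor clarification.

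**What to change.** 1. In Section 8.1.1, limit the ET exclusion to summaries by timepoint.
2. In Section 8.7.4, add ET postdose values as a fourth type beside original, repeat and unscheduled values.
3. As a minor clarification in Section 8.1, say that listings include ET data and any data collected after discontinuation, flagged as such, in line with the rule that all adverse events are listed.

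While Section 8.1.3 is open, its pointer for the outlier analysis to Section 10.7.4 should be corrected to 8.7.4, since no Section 10.7.4 exists.

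The cost is a few sentences and a listing flag, with no new data. The one drawback is that ET values come at varying times after dosing. That matters little for a worst-value summary, which already mixes times.

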## 8.1.2. Triplicate Readings

For vital signs data only, where triplicate readings are taken, the median of triplicate readings will replace the original readings in all calculations.

For electrocardiogram (ECG) data only, where triplicate readings are taken, the mean of triplicate readings will replace the original readings in all calculations.

In case of incomplete triplicate readings (eg, only 2 out of 3 readings were recorded), the mean and/or medians will be calculated based on the number of readings available.

## 8.1.3. Repeat and Unscheduled Readings

For vital signs and ECG data only, any predose value recorded in addition to the original value or a postdose value recorded within 15 minutes of the original value will be defined as a repeat value; any postdose value recorded more than 15 minutes after the original value will be defined as an unscheduled value. For all other data types (eg, laboratory parameters), any value recorded in addition to the original value will be defined as an unscheduled value.

The original value will be replaced by the last associated repeat value in all calculations, with the exception of the ECG outlier analysis (see Section 8.7.4).

As unscheduled values are not associated with any scheduled timepoint, they will be excluded from all calculations, with the exception of the baseline derivation (see Section 8.1.4) and ECG outlier analysis (see Section 10.7.4).

## 8.1.4. Definitions of Baseline and Change from Baseline

The baseline will be defined as the last value recorded prior to dosing (Part A) or the first dose (Part B). If the date/time of the value is incomplete or missing, it will be excluded from

Covance Study: 8379789 Protocol Reference: OLP-1002-001

the baseline calculation, unless the incomplete date/time indicates the value was recorded prior to dosing (Part A) or the first dose (Part B).

Individual changes from baseline will be calculated by subtracting the individual subject's baseline value from the value at the timepoint. The mean change from baseline will be defined as the mean of the individual changes from baseline for all subjects.

See Section 8.1.3 for more detail on handling repeat and unscheduled readings in the calculations. See Section 8.1.2 for more detail on handling of triplicate readings in the calculations.

#### 8.2. Subject Disposition and Population Assignment

Subject disposition and population assignment will be listed.

A summary table by treatment will be provided, based on the all subjects population.

## 8.3. Screening Demographics

The screening demographics including age, sex, race, ethnicity, height, body weight, and body mass index will be listed.

A summary table by treatment will be provided, based on the safety population.

#### 8.4. Prior and Concomitant Medication

Prior medication will be defined as medication that ends prior to dosing (Part A) or the first dose (Part B). Concomitant medication will be defined as medication that starts after dosing (Part A) or the first dose (Part B) or starts but does not end prior to dosing (Part A) or the first dose (Part B).

Prior and concomitant medications will be coded using the World Health Organization Drug Dictionary (WHODrug) Global, Format B3, Version March 2018 (or later if upversioned during the study). Prior and concomitant medications will be listed.

#### 8.5. Pharmacokinetic Assessments

## 8.5.1. Pharmacokinetic Analysis

The following PK parameters will be determined where possible from the plasma concentrations of OLP-1002 using non-compartmental methods performed using Phoenix WinNonlin (Version 8.1 or higher):

#### Part A

Parameter	Definition	
AUC 0-tlast area under the plasma concentration-time curve from time 0 to the time of last		
	quantifiable plasma concentration (t last ), calculated using the linear trapezoidal ru	
	for increasing plasma concentrations and the logarithmic rule for decreasing plasma	
	concentrations	

$AUC_{0-\infty}$ % $AUC_{extrap}$	area under the plasma concentration-time curve from time 0 extrapolated to infinity percentage of AUC that is due to extrapolation from the last measurable plasma
-	concentration to infinity
$C_{max}$	maximum observed plasma concentration
$t_{max}$	time of maximum observed plasma concentration
t 1/2	apparent plasma terminal elimination half-life

## Part B

Parameter	Definition		
AUC 0-τ	area under the plasma concentration-time curve calculated over the dosing interval		
	$(\tau)$		
$\mathrm{AUC}_{0\text{-}\infty}$	area under the plasma concentration-time curve from time 0 extrapolated to infinity		
$%AUC_{extrap}$	percentage of AUC that is due to extrapolation from the last measurable plasma		
	concentration to infinity		
$C_{max}$	maximum observed plasma concentration		
$C_{trough}$	concentration observed at the end of the dosing interval		
$t_{max}$	time of maximum observed plasma concentration		
$t_{1/2}$	apparent plasma terminal elimination half-life		
$RAAUC_{0-\tau}$	observed accumulation ratio based on AUC 0-τ , calculated as AUC 0-τ on profile day		
	15 / AUC 0-τ on profile day 1		
$RAC_{max}$	observed accumulation ratio based on C max , calculated as C max on profile day 15 /		
	C max on profile day 1		
TCP	temporal change parameter, calculated as $AUC_{0-\tau}$ on profile day 15 / $AUC_{0-\infty}$ on		
	profile day 1		

The DN AUC0-∞, DN AUC0-tlast and DN Cmax will be calculated by dividing the original PK parameter by dose.

Additional PK parameters may be determined where appropriate.

The PK analysis will, where possible, be carried out using actual postdose times recorded in the raw data. If actual times are missing, nominal times may be used.

Concentrations are used as supplied by the analytical laboratory for PK analysis. The units of concentration and resulting PK parameters, with amount or concentration in the unit, will be presented as they are received from the analytical laboratory.

Cmax and tmax will be obtained directly from the plasma concentration-time profiles.

For multiple peaks, the highest postdose concentration will be reported as  $C_{max}$ . In the case that multiple peaks are of equal magnitude, the earliest  $t_{max}$  will be reported.

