#### **4.2. Part B**

Part B will comprise a multiple-dose, sequential-group study. Overall, 32 subjects will be studied in 4 groups (Groups B1 to B4), with each group consisting of 8 subjects. Up to 2 additional groups (16 subjects in total) may be included for further assessment of safety and tolerability.

Potential subjects will be screened to assess their eligibility to enter the study within 28 days prior to the first dose administration. Each subject will participate in 1 treatment period only and reside at the CRU from Day -1 until Day 15.

All subjects will return for non-residential visits on Days 18 ( $\pm 2$  days), 22 ( $\pm 2$  days), 25 ( $\pm 2$  days), and 29 ( $\pm 2$  days), and for a poststudy visit on Day 57 ( $\pm 2$  days).

In each of Groups B1 to B4, 6 subjects will receive OLP-1002 and 2 subjects will receive placebo. For all subjects, a single SC dose will be administered on Days 1, 4, 7, 10, and 13. Prior to each dosing occasion a physician will review the available safety and tolerability data from each subject to confirm it is acceptable to continue dosing. The dosing frequency in Part B may be changed following review of data from groups in Part A.

Sentinel dosing will only occur in Part B at dose levels where exposure to OLP-1002 at steady state is predicted to exceed exposures that have been shown to be safe and well

Covance Study: 8379789

[figure not shown]
tolerated in earlier groups in Parts A or B. In the event of sentinel dosing, 2 subjects (1 active, 1 placebo) will be dosed at least 4 days prior to the remaining 6 subjects (5 active: 1 placebo). Safety data for the sentinel subjects from at least 2 additional doses will be reviewed prior to dosing the remaining subjects (i.e. sentinel subjects' safety data after doses 1 and 2 will be reviewed prior to the remaining subjects receiving dose 1). In addition, safety data from each subject will be reviewed by a physician prior to each dose to approve continued dosing.

Doses will be administered in an escalating manner following satisfactory review of safety, tolerability, and PK data up to Day 22 (216 hours post-final dose) from the lower dose levels. Part B may start after a review of the safety, tolerability, and available PK for Groups A1 to A6. The total daily dose administered will not exceed the highest single dose given in Part A.

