## 8.5.1.4. Anomalous Values

- If a value is considered to be anomalous due to being inconsistent with the expected PK profile, it may be appropriate to exclude this point from the PK analysis. However, the exclusion of data must have strong justification and will be documented in the raw data and CSR.
- Embedded BLQ values may be considered anomalous depending on the route of administration and the characteristics of the drug.
- Positive predose value(s) >5% of Cmax may be excluded from the summary statistics of PK tables and statistical analysis at the discretion of the pharmacokineticist.

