**CONFIDENTIAL** 

#### 9. INTERIM ANALYSES

In Part A, doses will be administered in an escalating manner following satisfactory review by the Sponsor and Investigator of the safety, and tolerability data up to Day 10 (216 hours postdose) from groups that received lower doses of OLP-1002. For escalation to doses ≥12 µg, PK data up to Day 7 (144 hours postdose) will also be reviewed. All available safety, tolerability, and PK data from previous groups will be reviewed prior to dose escalation.

In Part B, doses will be administered in an escalating manner following satisfactory review of safety, tolerability, and PK data up to Day 22 (216 hours post-final dose) from groups that received lower doses of OLP-1002. Doses may be reduced and may be lower than the starting dose. Available safety, tolerability, and PK data from all previous groups will be reviewed prior to dose escalation.

Dose escalation in Part A will only occur if data from a minimum of 4 subjects (Groups A1, A3, A5, A7, and A8) or 6 subjects (Groups A2, A4, A6, A9, A10, and A11) have been reviewed from the previous lower dose group, such that data from a minimum of 3 or 4 subjects, respectively, who have received OLP-1002 will be used to make the dose-escalation decision. Dose escalation in Part B will only occur if data from a minimum of 6 subjects have been reviewed from the previous lower dose group, such that data from a minimum of 4 subjects who have received OLP-1002 will be used to make the dose-escalation decision.

The justification for this is as follows:

- The study drug is of a known pharmacological class for which the on-target effects in humans are well characterized. Based upon nonclinical data, no clinically important off-target effects are expected within the proposed dose range.
- A minimum of 3 subjects receiving the active drug is considered sufficient to characterize the safety profile for OLP-1002.

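### Part B accumulation ratios and TCP take their numerator from profile day 15, but the stated schedule gives the last dose on Day 13, so no dosing interval starts there

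*SAP*

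**What the plan says.** The Part B table in SAP Section 8.5.1 gives formulas for three ratios:

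- RAAUC~0-τ~: AUC~0-τ~ on profile day 15 over AUC~0-τ~ on profile day 1.
- RAC~max~: "observed accumulation ratio based on C max , calculated as C max on profile day 15" over the profile day 1 value.
- TCP: AUC~0-τ~ on profile day 15 over AUC~0-∞~ on profile day 1.

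The same table defines AUC~0-τ~ as the area over the dosing interval. The SAP does not define the term profile day.

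The schedule is given in three other places:

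- Section 4.2: "For all subjects, a single SC dose will be administered on Days 1, 4, 7, 10, and 13".
- The footnote that Section 6.2 prescribes for all applicable Part B outputs: "Dosing regimen was a single subcutaneous dose administered on Days 1, 4, 7, 10 and 13".
- The escalation reviews in Sections 4.2 and 9, which both use "Day 22 (216 hours post-final dose)" as their data cut.

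Otherwise Day 15 appears only in Section 4.2, as the end of the residential stay. Section 3.2 lists six Part B secondary PK endpoints: C~min~, t~max~, t~1/2~, RAAUC~0-τ~, RAC~max~ and TCP.

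**The concern.** An accumulation ratio compares like with like: exposure over a full interval after a late dose against exposure over the same interval after the first dose. That needs a numerator profile that begins at a dose. All three formulas point to a day with no dose under the stated schedule, so this is not a slip in a single row.

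At stake are half of the listed Part B secondary PK endpoints. If someone programs the formulas literally, the reported ratios could suggest little or no accumulation where there is some, and TCP could suggest time-dependent kinetics where there are none. If someone instead notices and substitutes another profile, the report departs from the written definition without the SAP having authorised it.

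**Working it through.** **Step 1: reproduce the plan's own anchor.** With a last dose on Day 13, Day 22 is (22 − 13) × 24 = 216 h after it, which matches Sections 4.2 and 9. With a last dose on Day 15 it would be (22 − 15) × 24 = 168 h, which does not match.

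**Step 2: place Day 15.** The doses on Days 1, 4, 7, 10 and 13 are 3 days apart, so τ = 72 h. The last interval runs from Day 13 to Day 16. Day 15 is (15 − 13) × 24 = 48 h into it. No interval starts on Day 15, so AUC~0-τ~ on that day conflicts with its own definition in the same table.

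**Step 3: what a literal reading could produce.**

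- *Not calculable.* Subjects leave the unit on Day 15 and return on Day 18 (±2 days). Section 8.5.1.3 requires at least three consecutive quantifiable concentrations, one of them after C~max~. Section 8.5.1.1 excludes a profile that is entirely BLQ. A window starting on Day 15 may fail these rules. The sampling times are not in the SAP.
- *Calculable but too low.* A window starting 48 h after the last dose catches the decline, unless absorption is slow enough for concentrations still to be rising.

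**Step 4: illustrative size of the second case.** Assumptions, none from the SAP: one compartment, linear kinetics, absorption rate 0.5/h, five doses at 0, 72, 144, 216 and 288 h. Let F(t) be the single-dose AUC from 0 to t, and S(t) the sum of F over the five doses, each shifted to its dosing time.

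- RAAUC~0-τ~ from the last-dose profile: [S(360) − S(288)] / F(72).
- RAAUC~0-τ~ read literally, as 72 h from Day 15: [S(408) − S(336)] / F(72).
- TCP: the same numerators over F(∞).
- RAC~max~: the peak in the same windows over the first-dose peak.

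| Assumed t~1/2~ | RAAUC~0-τ~, last dose vs Day 15 | RAC~max~, last dose vs Day 15 | TCP, last dose vs Day 15 |
|---|---|---|---|
| 24 h | 1.15 vs 0.31 | 1.15 vs 0.36 | 1.00 vs 0.27 |
| 48 h | 1.56 vs 0.81 | 1.56 vs 0.88 | 0.99 vs 0.51 |
| 72 h | 1.98 vs 1.27 | 1.96 vs 1.35 | 0.97 vs 0.62 |

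Over a wider range, RAAUC~0-τ~ is 1.02 vs 0.07 at 12 h and 3.08 vs 2.55 at 168 h.

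**Step 5: hand check with near-instant absorption.** With k = ln 2 / t~1/2~, the true ratio is (1 − e^(−360k)) / (1 − e^(−72k)), and the Day 15 version is that times e^(−48k). At 24 h, e^(−72k) = 0.125 and e^(−48k) = 0.25, so the ratio is 1 / 0.875 = 1.14 and the Day 15 version is 1.14 × 0.25 = 0.29. At 48 h the pair is 1.54 vs 0.77. These are close to the table.

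If only the remaining 48 to 72 h of the last interval were used, the same simple model gives AUC ratios of 0.16 at 24 h and 0.35 at 48 h.

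**The case against.** The strongest defence is that no competent pharmacokineticist would compute an AUC~0-τ~ from a day without a dose: the instruction contradicts its own definition, so it would be queried and the last-dose profile used. That is plausible, but it concedes the point. The SAP does not define profile day, and Section 1 makes the SAP the template for the study report.

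A second defence is that Section 4.2 lets the Part B dosing frequency change. Day 15 would be a dosing day under a 2-day or 7-day interval, so the label may come from another schedule. That is inference. No section states a Day 15 dose, and the prescribed footnote fixes the five days. If the schedule had changed, the footnote and the 216-hour figure would need correcting instead.

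A third defence concerns importance, and it stands. PK is exploratory and to be determined where possible, these are secondary PK parameters, and no inferential analysis is planned. Section 8.5.3 lists all concentrations and parameters, so the ratios could be recomputed.

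Three stronger readings are not supported:

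- A reader might infer that understated accumulation would mislead dose escalation. Sections 4.2 and 9 say that PK data are reviewed, but neither names these ratios as an input.
- A reader might infer that downward bias is certain. The ratio may instead be missing or queried.
- A reader might add that Section 8.5.1.4, on predose values above 5% of C~max~, makes matters worse by removing Part B troughs. That is a separate, discretionary permission under anomalous values, and C~trough~ is itself a planned Part B parameter.

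**Conclusion.** The formulas for RAAUC~0-τ~, RAC~max~ and TCP contradict the SAP's own Part B schedule and are wrong as written. This rests on day arithmetic alone and needs no pharmacokinetic assumption.

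The consequence is less certain. The direction is downward only if concentrations are falling by 48 h after the dose, and the size depends on a half-life and absorption rate that the SAP does not give. Under the model shown, literal RAAUC~0-τ~ falls below 1 at the modelled half-lives up to 48 h, although linear accumulation cannot do so. At 72 h and above it exceeds 1 but is still too low.

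This should be corrected before database lock. It does not affect the AE, vital sign, ECG, laboratory or injection site analyses, and the exposure-limit primary endpoint in Section 3.1 does not mention these ratios.

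**What to change.** Reconcile the Part B table in Section 8.5.1 with Section 4.2 and the Section 6.2 footnote. In all three definitions, replace profile day 15 with the profile after the final dose actually given, with AUC~0-τ~ taken over the interval that starts at that dose. Under the schedule now stated, that is the Day 13 profile with τ = 72 h. This wording stays valid if the dosing frequency changes, provided the footnote is updated to match.

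Before finalising, check the PK sampling schedule to confirm that a full profile is collected after the final dose. The SAP does not show this. If it is not, the SAP should say which of the ratios can be derived. Also define profile day once.

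The cost is three table cells and one definition. The wording change itself needs no new data and leaves dosing untouched.
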